1. the patient takes study drug according to the originally assigned dose for at least 5 consecutive days prior to the PK sampling day (except for Cycle 1 Day 1 in dose escalation and expansion phases), AND no vomiting occurs within 4 hours following the last dose intake prior to the PK sample draw,
2. For the pre-dose or 24 hour post-dose sample, draw must occur between 0 to 6 hours before the dose that is immediately after, AND
3. The patient takes study drug under the originally assigned prandial conditions, i.e., dose administered without food for patients in the fasted cohort, or dose administered with light snack food for patients in the fed cohort, for at least 5 consecutive days prior to the PK sampling day (except for Cycle 1 Day 1), AND Additionally, a sample can be considered non-evaluable as per scientific judgment of the clinical pharmacology expert even if the above criteria are fulfilled. Reason will be documented.

A patient belongs to PAS if he/she has either an evaluable full PK profile or an evaluable trough PK sample.

Any blood samples missing blood collection date or time, or missing associated study drug dosing date or time will be excluded.

Frequency counts and percentages (using FAS as denominator) of patients in each of the above defined analysis sets will be summarized. In addition, listings of patients included in each of the analysis sets will be provided.

Section 2.3.5 provides further details regarding the derivation of the analysis sets.

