Concentration values below the lower limit of quantitation (LLOQ) (< 1.0 ng/mL) will be displayed in listings as zero with a flag and handled as zero in the calculations of summary statistics except for geometric means and associated CVs where they will be set to missing. Any missing PK parameters will not be imputed.

LDK378 concentrations

Summary statistics, including n, mean, SD, coefficient of variation CV (%) for mean, geometric mean, geometric CV (%), median, minimum and maximum, will be presented for evaluable PK plasma concentration of LDK378 following the general reporting rule for PK, by treatment and scheduled time point for both full PK profile and trough PK concentrations, separately for fasted and fed patients and for escalation phase and expansion phase. For patients with full PK profile on Cycle 1 Day 1 or Cycle 2 Day 1, corresponding graphical presentations of the plasma concentration profiles will be provided by treatment using arithmetic mean (+/- SD) and geometric mean values at each scheduled time point. The individual plot will also be provided.

LDK378 PK parameters

Primary and secondary PK parameters will be summarized using the same reporting approach as for LDK378 concentrations, by treatment, separately for Cycle 1 Day 1 and Cycle 2 Day 1 for fasted and fed patients in the escalation and expansion phase. For Tmax, only median, minimum and maximum will be presented.

All PK parameters and concentration data will be listed by treatment using PAS.

Dose proportionality (DP) analysis

DP analysis at single dose (Cycle 1 Day 1) and steady state (Cycle 2 Day 1): Data from both dose-escalation phase and expansion phase will be used. AUC0-24h and Cmax will be analyzed. All dose levels will be included.

DP will be assessed via the following model as well as graphical presentations.

DP is analyzed by fitting a linear model as described below.

$$\ln(\text{PK}) = \alpha + \beta * \ln(\text{actual dose}),$$

where PK is the PK parameter, AUC₀₋₂₄ or C_{max}, and actual dose (mg/m²) is defined as dose divided by BSA.

The estimate and its 90% confidence interval (CIs) for β in each case are reported. As an informal comparison, the estimates and CIs for β are compared to the target dose-proportionality range, calculated by the following formula (Smith, 2000).

Lower bound of target dose-proportionality range of β : $1 + \ln(0.8)/\ln(\text{dose range})$

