Upper bound of target dose-proportionality range of β : $1 + \ln(1.25)/\ln(\text{dose range})$

Dose range is the highest actual dose/lowest actual dose, for which data are used for the dose proportionality analysis. The dose range may or may not be the same for all parameters.

This analysis is not prospectively powered for the result to fall into the target range, and therefore the actual result rather than the comparison itself should be emphasized when interpreting data.

Trough concentration (C_{trough})

Trough PK samples will be collected at the following time points:

- 0 hour pre-dose samples on C1D1, C1D8, C1D15, C2D1-C6D1 in all patients
- 0 hour pre-dose sample on C1D2 (i.e. 24 hour post-dose samples on C1D1), and C2D2 (i.e.

24 hour post-dose samples on C2D1) for patients with full PK collection

The trough concentrations obtained throughout the study will be plotted over time by treatment arm using PAS. Only time points with $n \geq 4$ trough observations will be shown on the figure.

No model-based analyses will be conducted.

Average C_{trough}

Average trough concentration will be used in the exposure response analyses. Each patient may have one or more C_{trough} values. The average C_{trough} considering the distribution of PK is generally lognormal is defined as:

$C_{trough_{avg}} = \text{geometric mean (all } C_{trough} \text{ for each patient)}$, considering the distribution of PK concentration is generally lognormal.

Ceritinib trough concentration included in calculating the average **must fulfill** the following rules:

- For the pre-dose or 24 hour post-dose sample, draw must occur between 18 to 30 hours

after the last dose intake (except for Cycle 1 Day 1), AND

- For the pre-dose or 24 hour post-dose sample, the draw must occur before the next dose

intake, AND

- Additionally, a sample can be considered non-evaluable as per scientific judgment of the

clinical pharmacology expert even if the above criteria are fulfilled. Reason will be documented.

The criteria have been modified over evaluable trough concentration as defined in PAS by removing the following three rules:

- No vomiting occurs within 4 hours following the last dose intake prior to the PK sample draw,
- The patient takes study drug according to the originally assigned dose for at least 5 consecutive days without interruption or dose modification prior to the PK sampling day (except for Cycle 1 Day 1),

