- The patient takes study drug under the originally assigned prandial conditions, i.e., dose

administered without food for patients randomized to the treatment arm of 750 mg fasted, or dose administered with food for patients randomized to the treatment arm of 450 mg with low-fat meal or 600 mg with low-fat meal, for at least 5 consecutive days prior to the PK sampling day (except for Cycle 1 Day 1)

This allows exposure-response analyses to take into account the exposure after study drug interruption, dose reduction, vomiting or fail to adhere to the assigned prandial condition for individual patient.

Quartile ranges of C_{trough_avg} are defined as:

- <Q1: <25th percentile
- Q1-<Q2: ≥25th percentile and <50th percentile
- Q2-<Q3: ≥50th percentile and <75th percentile
- ≥Q3: ≥75th percentile

C_{trough_avg} and its quartile values will be used in display of AE.

Inter and intra patient variation

The intra-patient and inter-patient variations will be evaluated using data from patients at MTD with one or more than one evaluable steady state trough PK measurements. Evaluable trough concentration is defined in PAS. For steady state trough concentration, we will only consider trough values collected on or after C1D15 (C1D1 sample will not be used in the analysis). The intra-patient and inter-patient variations will be estimated using random effects model with treatment as a fixed effect and patient as a random effect. See [Section 5.7](#) for more details.

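### The average trough used for the adverse-event display includes a first-dose sample taken only in escalation, so it depends partly on study part and time on drug

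*SAP*

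**What the plan says.** SAP 2.10 (Average Ctrough) defines the patient-level exposure measure as the geometric mean of all of that patient's troughs. A sample counts if it meets the timing rule, "For the pre-dose or 24 hour post-dose sample, draw must occur between 18 to 30 hours" after the last dose, and is drawn before the next dose. The clinical pharmacology expert may also reject a sample. The measure and its quartiles are then used to display adverse events.

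The trough list in the same section includes the "0 hour pre-dose sample on C1D2 (i.e. 24 hour post-dose samples on C1D1), and C2D2" samples for patients with full PK collection.

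The definition of an evaluable trough in SAP 2.2 is stricter. Among other things it requires that "the patient takes study drug according to the originally assigned dose for at least 5 consecutive days prior to the PK sampling day", with an exception for Cycle 1 Day 1. For the average, SAP 2.10 relaxes this: "The criteria have been modified over evaluable trough concentration as defined in PAS by removing the following three rules". The rules dropped concern vomiting, five days at the assigned dose, and prandial condition. The reason given is: "This allows exposure-response analyses to take into account the exposure after study drug interruption, dose reduction, vomiting" or failure to keep to the prandial condition.

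The next paragraph of SAP 2.10, on inter- and intra-patient variation, uses only troughs from Cycle 1 Day 15 onward. The average carries no such limit.

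**The concern.** A sample taken 24 hours after the first dose of a drug that accumulates several-fold is not comparable with a steady-state trough. Here only one study part contributes it, and its weight in the average grows as the number of later troughs falls. The measure then reflects three things: true exposure, study part, and how long the patient stayed on drug.

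Time on drug is itself linked to adverse events, and the link can run either way:

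- If patients with events stop early, they are pushed into low quartiles and a real exposure trend looks weaker.
- If events accrue with time on drug, patients who leave early read low and have had little time for an event. A trend can then look stronger, or appear where there is none.

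**Working it through.** **1. Which samples exist.** Protocol Table 7-1 marks Cycle 1 Day 2 as escalation only, and Table 7-5 lists it for escalation. SAP 2.10 gives expansion a full profile at Cycle 2 Day 1 only. Blood volumes are consistent with this: 13 escalation samples at 1 mL is the stated 13 mL, and the 8 expansion samples in SAP 2.10 (five around Cycle 2 Day 1, plus Day 1 of Cycles 1, 3 and 4) make the stated 8 mL. This is corroboration only, since Amendment 6 dropped one expansion sample and the expansion log (Table 7-6) is not in the public text.

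**2. Does Cycle 1 Day 2 enter?** It is on the trough list, falls inside 18 to 30 hours and precedes the second dose. Nothing mandatory excludes it. The pre-dose Cycle 1 Day 1 sample is not a problem: values below the quantification limit count as zero "except for geometric means and associated CVs where they will be set to missing".

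**3. Effect on one patient.** Let S be the steady-state trough, R the ratio of steady state to first dose, and k the number of usable troughs, one of them Cycle 1 Day 2. Then

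average = (S/R × S^(k−1))^(1/k) = S × R^(−1/k).

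The full escalation schedule gives k = 6 (C1D2, C1D15, C2D1, C2D2, C3D1, C4D1). Values of R:

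- 6.2: adult AUC accumulation ratio at 750 mg (Protocol 1.2.1.2.4), as a proxy for the trough ratio.
- 2.7: linear kinetics with the 36-hour half-life in Protocol 2.3, 1/(1 − 2^(−24/36)) = 2.70.

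| Usable troughs | R = 6.2 | R = 2.7 |
|---|---|---|
| k = 1 (C1D2 only) | 0.16 | 0.37 |
| k = 2 | 0.40 | 0.61 |
| k = 6 | 0.74 | 0.85 |
| Expansion, protocol schedule | 1.00 | 1.00 |

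If the SAP's longer list of nine troughs were collected (including C1D8, where the adult ratio is 4.7), escalation would read ((1/6.2) × (4.7/6.2))^(1/9) = 0.79 and expansion (4.7/6.2)^(1/8) = 0.97.

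**4. Placement in quartiles.** Amendments 6 and 8 give 40 escalation patients of 83, so 43 in expansion. With equal true exposure, complete sampling, R = 6.2 and an assumed log-scale SD of 0.6, escalation patients are 48% of the total but 64% of the lowest quartile and 32% of the highest.

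**5. Effect on the display, pooled.** These are simulations with an assumed overall event rate of 25%; R = 6.2, with R = 2.7 in brackets.

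- *Events accrue with time on drug, no exposure effect.* With the adult median exposure of 26.9 weeks (Protocol 1.2.1.2.1), the spurious top-minus-bottom gap is about 4 points (2.5). With an assumed 9-week median it is about 11 (7.5). Using only troughs from C1D15 it is about 0 in both. With a true effect added, the gap at R = 6.2 is about 30 against 29 with the restriction (26.9 weeks), and 37 against 32 (9 weeks).
- *Patients with events stop early* (assumed: 10% of them, 5% of others, before C1D15). True quartile rates of 13/20/27/40% become 15/19/26/38%. The gap falls from 27 to about 22 (24); with the restriction it is 26.

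**6. Sampling error of the gap.** At a 25% rate and n/4 patients per quartile, SE = sqrt(2 × 0.25 × 0.75/(n/4)). For n = 83 it is 13 points; for n = 42 to 45, about 18 to 19; for n = 13 to 23, about 26 to 34. The smaller sizes are the possible ranges for the 500 mg/m² fed and 510 mg/m² fasted groups.

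**The case against.** **The display is descriptive and the distortion is below its sampling error.** This stands, and it sets the severity. It does not justify keeping a systematic error that the plan can remove in a sentence.

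**The average is meant to show realised exposure, so a patient who stops in week one should read low.** This fails. An expansion patient with the same exposure has no such sample, so the measure does not treat equal exposure equally. The stated aim of the relaxation covers interruption, reduction, vomiting and prandial deviation, not a first dose.

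**The five-day rule may never have excluded this sample.** A reader might infer that dropping the rule plainly let Cycle 1 Day 2 in. On its plain reading the rule would exclude it, but the Cycle 1 Day 1 exception could be taken to cover a sample described as 24 hours after the Day 1 dose. The documents leave this open. Either way the sample is admitted to the average.

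**How quartiles are formed.** A reader might infer that the SAP leaves this wholly open. The documents do not support that: SAP 2.1 makes treatment group the default for safety and PK summaries, and parts of the SAP are blacked out. The default does not remove the problem, because the two RDE groups pool both parts and the dependence on time on drug remains within escalation-only groups.

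**By-group gaps.** In groups this small, simulated gaps show direction only; the standard errors above exceed any useful reading of their size.

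**Conclusion.** The point holds as a minor one. As written, the average admits a first-dose sample that only escalation patients have, and so reads low for them by an amount that depends on how many later troughs they reach. The formula follows from the SAP's definition. Its size rests on adult ratios (6.2 or 2.7) standing in for children and on treating troughs from C1D15 as steady state, which the adult data in Protocol 1.2.1.2.4 support.

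The effect on the quartile display can go either way. The spurious pooled gap of about 4 to 11 points at R = 6.2 depends on the assumed SD, event rate and time on drug, and lies below the 13-point standard error.

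A reader might infer that the dose recommendation or the efficacy conclusion is compromised. Neither uses this average: MTD/RDE rests on DLTs in the dose-determining set, and ORR on tumour response.

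**What to change.** - Define the average as the geometric mean of troughs on or after Cycle 1 Day 15, the limit SAP 2.10 already applies to the variability analysis. Keep the relaxed rules on interruption, dose reduction, vomiting and prandial condition. No protocol-scheduled post-dose expansion trough is lost.
- Show patients with no such trough, with their adverse events, in a separate row beside the quartiles.
- Separately, reconcile carried-over text. The SAP trough list, "0 hour pre-dose samples on C1D1, C1D8, C1D15, C2D1-C6D1 in all patients", includes C1D8, C5D1 and C6D1, which are not in Protocol Table 7-5. The SAP also describes doses "administered without food for patients randomized to the treatment arm of 750 mg fasted", and with low-fat meals at 450 and 600 mg; this study has no such randomised arms.

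**Cost.** Two sentences and one table row, plus some patients leaving the quartiles. With exponential time on drug of median m days, a share 1 − 2^(−t/m) stops before day t:

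- m = 188.3 (26.9 weeks): 5.0% before 14 days (escalation) and 7.4% before 21 days (expansion). Weighted 40:43, about 6% have no average, against about 4% under the current rule.
- m = 63 (9 weeks): 14.3% and 20.6%, so about 18%, against 11 to 12% now, depending on how days are counted.

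The quartiles are then selected on reaching a steady-state sample. The event rate among those left out could be high (40% in the early-stopping case) or low (1 to 3% when events accrue with time), so the quartiles must be read together with the extra row.

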|--------------------------------------|---------------------------|--------------------|
|                                      | All Grades
n (%)       | Grade 3/4
n (%) |
| Cough                                | 62 (24.3)                 | 0                  |
| Abdominal Pain Upper                 | 58 (22.7)                 | 2 (0.8)            |
| Dyspnea                              | 47 (18.4)                 | 8 (3.1)            |
| Asthenia                             | 45 (17.6)                 | 2 (0.8)            |
| Blood Alkaline Phosphatase Increased | 45 (17.6)                 | 13 (5.1)           |
| Back Pain                            | 43 (16.9)                 | 1 (0.4)            |
| Headache                             | 41 (16.1)                 | 3 (1.2)            |
| Weight Decreased                     | 39 (15.3)                 | 4 (1.6)            |
| Blood Creatinine Increased           | 39 (15.3)                 | 0                  |
| Pyrexia                              | 38 (14.9)                 | 0                  |
| Rash                                 | 32 (12.5)                 | 0                  |
| Insomnia                             | 31 (12.2)                 | 0                  |
| Dyspepsia                            | 26 (10.2)                 | 1 (0.4)            |
| Hypokalemia                          | 26 (10.2)                 | 11 (4.3)           |
| Dizziness                            | 26 (10.2)                 | 0                  |

Dose reductions due to adverse events occurred in 58.4% of patients treated with LDK378 at the 750 mg dose; 38.8% of patients had only 1 dose reduction. The most frequent AEs requiring dose adjustments or interruptions reported in  $\geq 5\%$  of the patients were: ALT increased, nausea, AST increased, vomiting, diarrhea, fatigue, and abdominal pain. Adverse events (AEs) leading to study drug discontinuations occurred in 10.2% of patients treated with LDK378 at the 750 mg dose. The most frequent AEs leading to study drug discontinuations were decreased appetite, pneumonia, ALP increased, pneumonitis, and respiratory failure.

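### The planned AE display by average-trough quartile counts troughs drawn after AE-driven dose changes, so it understates any exposure relation for AEs that alter dosing

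*SAP*

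**What the plan says.** SAP 2.10 (Average Ctrough) defines one exposure value per patient, the geometric mean of all that patient's troughs. Its uses are stated twice: "Average trough concentration will be used in the exposure response analyses", and, of the average, "and its quartile values will be used in display of AE".

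The sampling rules are looser than those of the pharmacokinetic analysis set (PAS): "The criteria have been modified over evaluable trough concentration as defined in PAS by removing the following three rules". The removed rules cover vomiting, prandial state and dose stability. The last reads: "The patient takes study drug according to the originally assigned dose for at least 5 consecutive days without interruption or dose modification". The stated reason is "This allows exposure-response analyses to take into account the exposure after study drug interruption, dose reduction", together with vomiting and departures from the assigned prandial state. One timing rule stays: "draw must occur between 18 to 30 hours" after the last dose. A draw during an interruption therefore drops out, and a draw after resumption at a lower dose stays in.

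The average is not cut off at AE onset or at the first dose change, and it is not restricted to steady state. SAP 2.8.1 counts each AE at its maximum grade, without reference to when the troughs were drawn. Protocol Table 6-4 requires interruption followed by a one-level reduction after many AEs (for example Grade 3 AST/ALT, Grade 3 or higher lipase/amylase, Grade 3 diarrhea). Table 6-3 gives the steps at the RDE: 500/510, then 400, 300 and 200 mg/m².

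**The concern.** A display of AEs by exposure quartile will be read for whether higher exposure brings more toxicity. That reading needs exposure to come before the event. Here part of the exposure value can come after the event and be caused by it: the AE leads to a reduction, the reduction lowers later troughs, the average falls, and the patient moves towards a lower quartile. Vomiting can act the same way without a dose change, since it is both an AE of special interest (SAP 2.8.1.1) and one of the relaxed sampling rules.

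Counting post-reduction exposure makes sense for outcomes that come later. For an AE that came first it is reverse causation. The risk is a flat or mildly inverse picture, read as reassurance about exposure and toxicity in children.

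**Working it through.** The plan gives no figure for this display, so there is nothing to reproduce. The check is on direction and size.

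**Inputs from the documents**
- First reduction step: 400/500 = 0.80; second step: 300/500 = 0.60 (Protocol Table 6-3).
- AE-driven reductions: "Dose reductions due to adverse events occurred in 58.4% of patients treated with LDK378 at the 750 mg dose" (Protocol 1.2.1.2.1). These are adult patients, with median exposure 26.9 weeks (about 188 days); 38.8% had only one reduction.
- Between-patient CV of 93% (AUClast) and 87% (Cmax), adult patients after a single dose (Protocol 1.2.1.2.4). Log-SD = √ln(1 + CV²) = 0.79 and 0.75.
- Accumulation ratio 4.7 at C1D8 and 6.2 at C2D1 (same section).
- 83 patients enrolled (Protocol, Amendment 8 rationale).

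**By hand.** If j of k troughs follow a reduction by factor r, the geometric mean is multiplied by r^(j/k). One step affecting half the troughs gives 0.8^0.5 = 0.89. Since ln 0.89 ≈ −0.11, the shift is 0.11/0.79 ≈ 0.14 SD, or 0.11/0.6 ≈ 0.19 SD if the log-SD is 0.6. Two steps affecting all troughs give 0.60.

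**Model 1 (AEs in general).** 400,000 patients per scenario; assumed AE rate 50%; troughs at C1D15, C2D1, C2D2, C3D1 and C4D1; assumed within-patient log-SD 0.25; onset uniform over Days 1-63 unless stated. AE rate by quartile when there is no true relation:

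| Share of AEs leading to reduction | Reduction | Log-SD | Lowest | Highest |
|---|---|---|---|---|
| 58.4%, onset spread over 26.9 weeks | 20% | 0.79 | about 51% | 49% |
| 20% | 20% | 0.79 | 51% | 49% |
| 58.4% | 20% | 0.79 | 53% | 48% |
| 58.4% | 20% | 0.6 | 54% | 47% |
| 100% | 20% | 0.6 | 56% | 44% |
| 58.4% | 40% | 0.6 | 58-59% | 43% |

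With a true odds ratio of 2 per SD, the true 30%-70% gradient becomes 34%-67% (20% reduction) or 39%-62% (40% reduction) at log-SD 0.6. It is about 31%-69% at log-SD 0.79 with late onset or with a 20% share.

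**Model 2 (only AEs that change dosing).** Overall rate 58%; every AE leads to interruption and then ×0.8, and 33.6% of these patients go on to ×0.6 (1 − 38.8/58.4 = 0.336); CV 75%, trough proportional to dose. Assumed: interruption 10 days, intra-patient CV 30%, onset mostly exponential with mean 45 days. Without the first-dose (C1D2) sample, over three sampling schedules, the odds ratio per doubling of trough is:

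| True | SAP average | Steady-state troughs before first dose-modifying AE |
|---|---|---|
| 1.0 | 0.80-0.85 | 1.00-1.01 |
| 1.25 | 0.99-1.06 | 1.23-1.24 |
| 1.5 | 1.17-1.24 | 1.46-1.47 |
| 2.0 | 1.52-1.62 | 1.92-1.94 |

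With N = 83 and a true odds ratio of 1.5 in this model, the chance that the top quartile shows no higher an AE rate than the bottom rises from 9% to 32%.

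**Check of remedies (Model 1, no true relation).** Steady-state troughs before the first dose modification give 47% and 47%. Troughs before AE onset (all troughs for patients without an AE) give 50% and 45% if C1D8 is included, and about 73% and 36% if C1D2 is included. Patients with an AE are then represented by early samples below steady state.

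**Patients without a qualifying trough.** In Model 1, with AE onset before C1D15 and a reduction: 0.5 × 0.584 × 14/62 ≈ 7%; if every AE leads to a reduction, 0.5 × 14/62 ≈ 11%. Model 2 gives 15-21%.

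**The case against.** Much of the other side stands.

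- **The 58.4% is a share of patients, not of AEs.** Using it as a per-AE probability is an assumption. Table 6-4 keeps the dose for many events, including Grade 1-2 nausea, Grade 1-2 AST/ALT (without marked bilirubin elevation), any-grade hypophosphatemia and Grade 1-3 neutropenia. Most adult AEs were low grade: diarrhea 85.9% at all grades, 5.9% at Grade 3/4.
- **Timing.** The adult rate accrued over a median of 26.9 weeks. Reductions after the last trough (C4D1 in Protocol Table 7-5, C6D1 in the SAP list) cannot enter the average.
- **Consequence.** The display is descriptive, and exposure-AE is not a listed objective. With about 83/4 ≈ 21 patients per quartile, the standard error of a between-quartile difference is √(2 × 0.25/20.75) ≈ 0.155, or about 16 points. A 7-point artefact is about 1.5 patients.
- **Visibility.** SAP 2.12 is redacted, so a companion exposure analysis there cannot be ruled out.

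These points limit the size and the scope. They do not remove the mechanism, which the SAP states as its intention, and no readable text pairs the display with another exposure measure or a caution. Sampling noise does not offset a bias that always acts in one direction.

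A reader might infer that the display will reverse a real exposure-toxicity relation, or that all AE displays are distorted. Neither is supported. A strong relation is flattened, not reversed, and AEs that do not change dosing or absorption carry almost none of this bias. Nor can the choice of dose be said to be compromised: the MTD/RDE rests on Cycle 1 DLTs in the dose-determining set and does not use this average.

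**Conclusion.** The concern holds for AEs that lead to a dose change or lower absorption before the last trough. For these, the average-trough display is biased towards no relation, and it can look inverse when the true relation is absent or weak. The direction was the same in every scenario run.

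The size is uncertain. For AEs taken together, the false gap between lowest and highest quartile runs from about 2 points to about 12 (20% reduction), or 15-16 if 58.4% of AEs lead to a 40% reduction. For dose-modifying AEs alone, a true odds ratio of 1.25 per doubling disappears almost entirely. These figures rest on adult reduction rates and adult PK variability, and on assumed AE rates, onset times and within-patient variation. The documents give no per-AE or pediatric reduction rate.

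This is a cheap improvement to a descriptive safety display, not a flaw in the primary analysis. One further reason to re-read the rule: its text on prandial state describes patients randomized to 750 mg fasted and 450 or 600 mg low-fat-meal arms, which this study does not have. It may have been carried over from another study.

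**What to change.** In SAP 2.10, for the AE display:

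1. Use the geometric mean of troughs from C1D15 onward (the steady-state cut-off the SAP already uses for inter- and intra-patient variation) drawn before the patient's first dose reduction or interruption. SAP 5.3 counts even a single 0 mg day for any reason as an interruption, so state whether every interruption or only AE-related ones end the averaging.
2. Keep the PAS vomiting rule for this display, because the cut at dose change does not deal with reduced absorption.
3. Show patients without a qualifying trough as a separate category. They are mostly patients with early AEs, and dropping them would lower the overall AE rate shown.
4. Keep the all-trough average as a secondary display, with a note that it includes exposure after AE-driven dose changes.

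Do not use pre-onset troughs that include C1D2 or C1D8. They lie below steady state and create their own inverse gradient.

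Cost: a few lines of SAP text and one extra derived variable. Roughly 7-21% of patients would have no value, and the vomiting rule would remove some further samples.
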